5.3.2. Transitioning to edoxaban at randomization

For subjects randomized to the edoxaban-based regimen that require switching from another anticoagulant the following algorithm should be used. Capture the date and timing of first study dose in eCRF.

Table 5.2: Transitioning to edoxaban at randomization

Switching to edoxaban		
From	To	Recommendation
VKA	edoxaban	Discontinue the VKA and start edoxaban when INR is < 2.5.
Other non-VKA OAC drugs • dabigatran • rivaroxaban • apixaban	edoxaban	Discontinue the OAC and start edoxaban at the time of the next OAC dose.
Parenteral anticoagulants	edoxaban	These agents should not be administered simultaneously. Subcutaneous anticoagulant (i.e. LMWH fondaparinux): discontinue subcutaneous anticoagulant and start edoxaban at the time of the next scheduled subcutaneous anticoagulant dose. Intravenous unfractionated heparin: Discontinue the infusion and start edoxaban 4 hours later.

5.3.3. Transition from edoxaban at EOT

For subjects randomized to the edoxaban-based regimen that require switching from edoxaban to another anticoagulant at the scheduled EOT (or due a premature edoxaban discontinuation) the following algorithm should be used.

Table S-5: Transitioning from Edoxaban at EOT		
Switching from edoxaban		
From	To	Recommendation
edoxaban	VKA	
During the transition from edoxaban to VKA continuous adequate anticoagulation should be ensured during any transition to an alternate anticoagulant.
 
Oral option:
 
 For subjects currently on a 60 mg once-daily dose, administer an edoxaban dose of 30 mg once-daily together with an appropriate VKA dose. For subjects currently on a 30 mg dose once-daily (for one or more of the following factors: moderate to severe renal impairment (CrCL 15 - 50 ml/min), low body weight, or use with certain P-gp inhibitors), administer an edoxaban dose of 15 mg once-daily together with an appropriate VKA dose. Edoxaban 15 mg once-daily is not indicated as monotherapy, as it may result in decreased efficacy. It is only indicated in the process of switching from edoxaban 30 mg once-daily to VKA, together with an appropriate VKA dose. 
Subjects should not take a loading dose of VKA in order to promptly achieve a stable INR between 2.0 and 3.0. It is recommended to take into account the maintenance dose of VKA if the patient was previously taking a VKA or to use valid INR driven VKA treatment algorithm, in accordance with local practice.
 
Once an INR 2.0 is achieved, edoxaban should be discontinued. Most patients (85%) should be able to achieve an INR 2.0 within 14 days of concomitant administration of edoxaban and VKA. After 14 days it is recommended that edoxaban is discontinued and the VKA continued to be titrated to achieve an INR between 2.0 and 3.0. It is recommended that during the first 14 days of concomitant therapy the INR is measured at least 3 times just prior to taking the daily dose of edoxaban to minimize the influence of edoxaban on INR measurements. Concomitant edoxaban and VKA can increase the INR post edoxaban dose by up to 46%.

		
Parenteral option: Discontinue edoxaban and administer a parenteral anticoagulant and VKA at the time of the next scheduled edoxaban dose. Once a stable INR of 2.0 is achieved, the parenteral anticoagulant should be discontinued and the VKA continued.

edoxaban	Other non-VKAOAC drugs	Discontinue edoxaban and start the non-VKA anticoagulant at the time of the next scheduled dose of edoxaban.

Switching from edoxaban		
From	To	Recommendation
edoxaban	Parenteral anticoagulants	These agents should not be administered simultaneously. Discontinue edoxaban and start the parenteral anticoagulant at the time of the next scheduled dose of edoxaban.

5.4. Vitamin K Antagonist (VKA)

An approved/ marketed VKA will be supplied as the preferred VKA for each selected country participating in the study. All VKA dispensations must take place through the IXRS that will provide the appropriate drug supply kit number.

In addition, the Investigator monitors the INR and adjusts the VKA dose to maintain the target INR between 2.0-3.0 inclusive. It is the Investigators responsibility to collect monthly INR assessments and record these throughout the study.

5.4.1. Dose

A preferred vitamin K antagonist (VKA) is selected for each participating country which is provided as study medication:-

Warfarin

Loading dose from 2 to 5 mg once-daily for 2-4 days followed by a maintenance dose of 2 to 10 mg once-daily adjusted by INR values to maintain target INR between 2.0 -3.0 inclusive.

Phenprocoumon

Weekly dose calculation of up to 9 mg on day 1, 6 mg on day 2 and maintenance doses between 1.5 to 6.0 mg once-daily thereafter, adjusted by INR values to maintain target INR between 2.0 -3.0 inclusive.

Fluindione

The initial daily dose of 20 mg is adjusted by INR values to maintain target INR between 2.0 -3.0 inclusive. In subjects at particular risk of bleeding (weight <50 kg, elderly, hepatic impairment), the initial dose is usually lower. No loading dose should be used.

The dose adjustment is performed in accordance to the package insert and usually by increments of 5 mg (1/4 tablet).

Acenocoumarol

The usual starting dose in a normal weight person is between 2 mg/day to 4 mg/day without administration of a loading dose, if the INR value before the start of treatment is within the normal range. Treatment may also be initiated with a loading dose regimen, usually 6 mg on the first day followed by 4 mg on the

second day. The maintenance dose generally lies between 1 and 8 mg once-daily, adjusted by INR values to maintain target INR between 2.0 -3.0 inclusive.

The dosing of the aforementioned VKAs must be individualized. The maintenance dose varies from subject to subject and its appropriateness must be checked individually on basis of INR values.

The Investigator or designee is responsible for dispensing the VKA antagonist and must ensure that drug supplied by Sponsor is used in accordance with the protocol and the VKA package insert.

5.4.2. Transitioning to Study VKA at Randomization

For subjects randomized to VKA who require switching from another anticoagulant (another VKA, other non-VKA OAC drugs or parenteral anticoagulants), follow the guidance for switching in the locally approved labels of these products. Capture the date and timing of first study dose in eCRF.

Table 5.4: Transitioning to Study VKA at Randomization

Switching to VKA		
From	To	Recommendation
Vitamin K Antagonist (VKA)	Study VKA	If the INR measured on the day of randomization is: 
 ≤ 2.5, start study VKA > 2.5, the Investigator or designee must recheck at a later time; start study VKA when the INR is ≤ 2.5; document the INR value and the date it was measured.
Other non-VKA OAC drugs 
 dabigatran rivaroxaban apixaban 	Study VKA	Ascertain adequate anticoagulation until an INR ≥ 2.0 is reached and then continue with study VKA only. Follow local label of country-selected VKA and label of NOAC being stopped for further guidance.
Parenteral anticoagulants	Study VKA	For subjects not previously on VKA, bridging with parenteral anticoagulation is permissible, but not recommended. For initiation of VKA therapy and related bridging with parenteral anticoagulation, follow locally established guidelines and local approved label (prescribing information) from the VKA manufacturer.

5.4.3. INR Management

Every effort should be made to optimize the VKA dosing and INR monitoring schedule to maintain INR values between 2.0-3.0 inclusive.

INR management is according to the standard of care and may be performed by the Investigator, the subject's primary care physician or other private physician, at

a specialized anticoagulation clinic or patient self-monitoring. Close attention to the INR management plan and frequent monitoring of INR values is strongly recommended to optimize the VKA treatment and maintain the subject's INR values between 2.0-3.0 inclusive. The Investigator will ensure the VKA is used according to the approved label (prescribing information).

Daily INR determinations upon initiation should be obtained until subject's INR is stable in the therapeutic range. It may take 4-14 days to attain the target - - therapeutic range of INR 2'.. 2.0.

Obtain subsequent INR determinations as per recommendations and guidelines provided in the local approved label from the respective VKA manufacturer.

5.4.4. Transition from VKA at EOT

Table 5.5: Transitioning to Study VKA at EOT

Switching from VKA		
From	To	Recommendation
Study VKA	VKA	When transitioning a subject to post-study VKA, either maintain the subject on the same maintenance dose or adjust the dose of VKA to maintain an TNR between 2.0-3.0 and follow the local guidelines for managing patients on VKA therapy.
Study VKA	Other non-VKA OAC drugs	When transitioning a subject to a newer non-VKA oral anticoagulant, switching guidance in the locally approved label of the non-VKA anticoagulant should be followed.

S.S. Clopidogrel (or alternative P2Y₁₂ antagonist)

The P2Y₁₂ antagonist clopidogrel is part of both the edoxaban-based and the VKA-based regimen. Please refer to Section 5.9 Labeling and Packaging.

5.5.1. Dose

Clopidogrel bisulfate 75mg once-daily as provided by sponsor.

In the presence of a documented clinical need (e.g. known hypersensitivity to clopidogrel or its excipients, known CYP2C19 poor metabolizer-clopidogrel non-responder, among others) the use of a P2Y₁₂ antagonist other than clopidogrel is allowed but must be pre-declared prior to randomization.

Either prasugrel [5 or 10 mg once-daily] or ticagrelor [90 mg twice-daily] may be used according to the regional clinical practice guidelines for the dose and administration of the respective P2Y₁₂ antagonist. The Investigator should follow

the relevant SmPC and the applicable regional guidelines regarding dose and transition from or to another P2Y₁₂ antagonist.

The 5 mg once-daily dose of prasugrel should be given as maintenance dose in subjects with body weight < 60 kg. The use of prasugrel in subjects > 75 years of age is generally not recommended but if treatment is deemed necessary, then a reduced maintenance dose of 5 mg once-daily should be prescribed in subjects in this age group. For additional details please consult the SmPC and the drug-- package insert.

Both prasugrel 5 or 10 mg once-daily and ticagrelor 90 mg twice-daily will be provided by the sponsor and dispensed through the IXRS. The Investigator or designee is responsible for dispensing the P2Y₁₂ antagonist through the IXRS and must ensure that drug supplied by sponsor is used only in accordance with the protocol and to the drug package insert.

5.5.2. Transitioning to study P2Y₁₂ antagonist at randomization

For subjects randomized to either the edoxaban-based or the VKA-based regimen discontinue the P2Y₁₂ antagonist being taken and start study clopidogrel (or . alternative study P2Y₁₂ antagonist) at the time of the next dose. Capture the date and timing of first study dose in eCRF.

5.5.3. P2Y₁₂ inhibitor non-bleeding related adverse drug effect

Subjects must follow the P2Y₁₂ antagonist pre-declared prior to randomization for 12 months. In the presence of a documented P2Y₁₂ antagonist drug specific side effect excluding bleeding, cross-over to another study P2Y₁₂ inhibitor is allowed.

A P2Y₁₂ inhibitor of similar potency is recommended wherever possible and if the treating physician considers it safe and the clinical situation allows doing so.

E.g.: subject on ticagrelor as pre-declared prior to randomization develops dyspnea as drug-specific side effect - cross-over to another P2Y₁₂ is allowed and prasugrel is recommended.

5.6. ASA

ASA is only part of the VKA-based regimen. Please refer to Section 5.9 Labeling and Packaging.

5.6.1. Dose

ASA 100 mg once-daily as provided by sponsor is administered in the VKA-based regimen for a minimum of 1 month and up to 12 months. In case the ASA dose before randomization was other than 100 mg once-daily, the dose has to be adjusted to 100 mg once-daily immediately after randomization. The duration of the ASA treatment in the VKA-based regimen is pre-declared by the Investigator prior to randomization guided by the clinical presentation (ACS or stable coronary disease), and upon the CHA₂DS₂-VASc and HAS-BLED score. The Investigator follows the applicable regional clinical guidelines (1).

The Investigator or designee is responsible for dispensing ASA through the IXRS and must ensure that drug supplied by sponsor is used only in accordance with the protocol and to the drug package insert.

ASA is prohibited in the edoxaban-based regimen throughout the 12 months of planned treatment.

5.6.2 Transitioning to study ASA at randomization -----

For subjects randomized to the VKA-based regimen only discontinue ASA as being taken and start study ASA at the time of the next dose. Capture the date and timing of first study dose in eCRF.

5.7. Interruptions and discontinuations of the assigned regimen

The intended duration of the two treatment regimens is 12 months (i.e., 365 days). Subjects stay on the assigned OAC-based regimen as much as possible.

Permanent discontinuation of the assigned regimen is mandatory if the CrCL falls below 15 mL/min on two consecutive occasions or if subject is placed on dialysis. If the Investigator doubts the accuracy of the CrCL value calculated with the Cockcroft-Gault formula, he/she may consider calculating CrCL using a 24 hour urine collection, for confirmatory purposes. If a subject's CrCL, calculated with either the Cockcroft-Gault formula or 24 hour urine collection, recovers to > 15 mL/min, the subject should resume study regimen in line with the applicable labels.

For subjects with a suspected transient decrease in CrCL < 15 mL/min it is recommended that repeat testing of CrCL occur after corrective action is taken or when the medical condition that caused the worsening renal function resolves. The timing of the repeat testing is at the discretion of the Investigator and will vary depending on the nature of the medical condition (e.g., 1-2 weeks for urinary tract infection or overdiuresis vs. several weeks to months for glomerulonephritis).

If other clinical contraindications for any study medication develop (according to the label of the respective drug), the study medication must be discontinued (or dosed decreased if applicable). If the contraindication resolves, the respective study medication is restarted. During each interruption of anticoagulant or antiplatelet therapy, subjects are evaluated to determine whether the subject can safely resume the study drug. A post-randomization change in health status that results in the subject meeting one or more of the exclusion criteria should only lead to interruption or discontinuation of the assigned medications if the change in health status implies a contraindication according to the drug labels.

Study medications are permanently discontinued if the subject refuses continuation of any medication in the assigned study regimens. If refusal of the subject is restricted to a single study drug, this drug is discontinued while the other drugs are continued unchanged.

All subjects are followed for 12 months irrespective of changes in the antithrombotic regimen. Clinical follow-up is only terminated at the explicit documented request of the subject (see Section 6.5).

All study medication start and stop dates are captured in eCRF together with the reason for interruption or discontinuation.

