Other completed studies include Phase I clinical pharmacology studies, Phase 2 dose-ranging studies in subjects with NVAF and subjects undergoing lower-extremity orthopedic surgery, and Phase 3 studies in subjects undergoing lower-extremity orthopedic surgery.

In the course of the edoxaban clinical development program, over 23,500 subjects have been given edoxaban encompassing over 34,100 subject-years of exposure.

The safety and efficacy of edoxaban has been evaluated in the following programs:

- Phase I studies (including 1627 subjects from pharmacokinetic (PK)-pharmacodynamic (PD) studies, PK in subjects with renal impairment, and drug-drug interaction studies): Results of these studies have shown that edoxaban is rapidly absorbed with rapid onset of action and the dose concentration relationship is generally linear. The mean terminal half-life ranges between 5 and 11 hours. The pharmacodynamic effect as measured by anti-Xa activity or inhibition of factor Xa activity lasts for 24 hours. Dose-related increases in PK concentrations and anti-thrombotic activity were observed, as measured by anti-Xa activity. The bioavailability is ~60% and 50% of the absorbed drug is excreted by renal clearance. The absorption, distribution, metabolism, and excretion are also mediated through the P glycoprotein (P-gp) transport system and drugs with P-gp inhibitory effects may alter edoxaban exposure.
- Phase 2 studies in AF subjects (including 1,952 subjects): These studies primarily evaluated safety of different dose regimens of edoxaban with approximately 12 weeks of treatment. Results of these studies showed that the twice a day (BID) regimen had higher

bleeding than once-daily regimen of edoxaban. Consequently, the once-daily regimen of edoxaban was tested in the subsequent Phase 3 trials.

- **Phase 3 pivotal trial** (ENGAGE AF-TIMI 48(13)) involving 21,105 subjects with a median follow-up of 2.8 years. Two once-daily regimens of edoxaban were compared with warfarin for the prevention of stroke and systemic embolism in patients with non-valvular atrial fibrillation. Both regimens were non-inferior to warfarin for the **prevention of stroke and systemic embolism and were associated with significantly lower rates of bleeding and death from cardiovascular causes**. Edoxaban has been approved for marketing in US and in Europe for this indication.

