Subject clinical visits are planned at 1, 3, 6, 9 and 12 months after randomization. All subjects have telephone assessments at 2, 4, 5, 7, 8, 10 and 11 months after randomization. All information must be captured in the eCRF and study assessments are performed according to the visit schedule provided under appendix Section 17.9. All subjects are followed for 12 months irrespective of changes in the antithrombotic regimen. Clinical follow-up is only terminated at the explicit request of the subject. All subjects on either edoxaban or VKA at 12 months, have a contact planned 1 month after the end-of-treatment visit, to collect data on targeted concomitant medications, SAEs, and other events of interest. The overall duration of subject participation from screening through follow-up is therefore approx. 13 months.

The study organization, including the CEC, DSMB, Executive Committee and Steering Committee are described in appendix section 17.1. An independent DSMB reviews pertinent study data to protect the safety of the subjects participating in the study.

Figure 3.1 Study Design

• Edoxaban dose reduction to 30 mg once-daily if either CrCL \leq 50 mL/min, or body weight \leq 60 kg, or concomitant therapy with certain P-gp inhibitors. • Clopidogrel 75mg once-daily (or in the presence of a documented clinical need prasugrel [5 or 10 mg once daily] / ticagrelor [90 mg twice daily] may be used). •• VKA of choice with dosing for target international normalized ratio (INR) of 2.0 - 3.0 inclusiveASA (100 mg once-daily) for 1-12 months guided by the clinical presentation (ACS or stable coronary disease), and upon the CHA₂DS₂-VASc and HAS-BLED score.
§ Goal of at least 25% ACS.

AF, atrial fibrillation; ACS, acute coronary syndrome; PCI, percutaneous coronary intervention; ISTH, International Society on Thrombosis and Haemostasis; CRNM, clinically relevant non-major; h, hours; d, days.

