5.3.1. Dose

Edoxaban 60 mg once-daily.

At randomization, the recommended dose of edoxaban is 30 mg once-daily in subjects with 1 or more of the following factors:

- Moderate or severe renal impairment (calculated CrCL 15 - 50 mL/min),
- Low body weight of < 60 kg (132 lbs),
- Concurrent use of P-gp inhibitors (please refer to local SmPC or to 1B, as applicable).

In EU countries, according to SmPC concomitant use of edoxaban with cyclosporine, dronedarone, erythromycin, or ketoconazole requires dose reduction to 30 mg once-daily. Concomitant use of edoxaban with quinidine, verapamil, or amiodarone does not require dose reduction.

All edoxaban dosage adjustments will be implemented through the IXRS. The IXRS will provide the appropriate drug supply kit number.

If low body weight (< 60 kg) present at randomization, the edoxaban dose is reduced permanently and even if the subject gains weight, the edoxaban dose remains reduced.

The dose of edoxaban returns to the regular dosage regimen of 60 mg once-daily any time the subject no longer displays any of the other above mentioned factors.

After randomization and in subjects without dose reduction, if subject's:

body weight drops to < 60 kg and the body weight change is > 10% of the subject's baseline body weight, then the edoxaban dose is reduced (i.e., to 30 mg once-daily) permanently.

CrCL becomes 15 to 50 mL/min and the CrCL change is > 20% of the subject's baseline CrCL, then the edoxaban dose is reduced.

Develops the need for concomitant treatment with certain P-gp inhibitors which require edoxaban dose adjustment, then the edoxaban dose is reduced (i.e., to 30 mg once-daily).

The dose of 15 mg edoxaban once-daily is not indicated as monotherapy and is solely provided as part of transition from edoxaban 30 mg at the end of study (see Section 5.3.3).

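### The post-randomization renal rules disagree on a first CrCL below 15 mL/min: neither the Section 5.3.1 dose reduction nor the Section 5.7 mandatory stop applies, while the Figure 3.1 note would reduce the dose

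*Combined protocol and SAP*

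**What the plan says.** Four places in the protocol bear on a fall in renal function.

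- **Section 5.3.1** (repeated in the synopsis under dosage form, dose and route). At randomization the renal factor for the lower edoxaban dose is "Moderate or severe renal impairment (calculated CrCL 15 - 50 mL/min"). For subjects not yet reduced, the later rule is "CrCL becomes 15 to 50 mL/min and the CrCL change is > 20% of the subject's baseline CrCL, then the edoxaban dose is reduced".
- **Figure 3.1 note** (Section 3.1). It begins "Edoxaban dose reduction to 30 mg once-daily if either CrCL" and gives 50 mL/min or less. It has no lower bound and no percentage condition.
- **Section 5.7, stop and resumption.** "Permanent discontinuation of the assigned regimen is mandatory if the CrCL falls below 15 mL/min on two consecutive occasions", or if dialysis starts. The same paragraph says that a subject whose CrCL recovers to more than 15 mL/min should go back on the study regimen, in line with the labels.
- **Section 5.7, repeat test.** For a suspected transient fall below 15, the recommendation is that "repeat testing of CrCL occur after corrective action is taken or when the medical condition that caused the worsening renal function resolves". Timing is left to the investigator. The examples run from 1-2 weeks to several weeks or months.

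CrCL is also checked at each on-site visit (Sections 6.2.1 and 6.2.3, and the notes to the Schedule of Events). A CrCL below 15 mL/min is exclusion criterion 11, and Section 6.1.2 has the IXRS accept only values of 15 or more at randomization.

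**The concern.** The 15 mL/min threshold closes the trial to a subject at entry, yet its first crossing after entry has no action of its own in the two sections that govern dosing and stopping. Read literally, those sections order a dose reduction for a moderate fall and nothing for a deeper one, until a second low value arrives.

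The primary endpoint is bleeding, and Section 1.1.1.5 states that "50% of the absorbed drug is excreted by renal clearance". Sites working from the Figure 3.1 note and sites working from Section 5.3.1 could handle the same subject differently. Edoxaban dose changes go through the IXRS, so whichever rule was programmed would decide the kit. The dose question concerns the edoxaban arm only. The permanent-versus-resume question concerns both arms, because Section 5.7 speaks of the assigned regimen.

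**Working it through.** The plan gives no figure to reproduce. The check codes the three numeric rules and applies them to the same subject.

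**Rules**
- A (Section 5.3.1 and synopsis): 15 ≤ CrCL ≤ 50 and change from baseline > 20%.
- B (Figure 3.1 note): CrCL ≤ 50.
- C (Section 5.7 mandatory stop): CrCL < 15 now and at the preceding measurement. Dialysis is set aside.

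**Illustration: subject on 60 mg, baseline CrCL 60 mL/min.** Fall = (60 − value)/60; for example (60 − 40)/60 = 33.3%.

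| Value (mL/min) | Fall | A | B | C |
|---|---|---|---|---|
| 40, first | 33.3% | yes | yes | no |
| 20, first | 66.7% | yes | yes | no |
| 15, first | 75.0% | yes | yes | no |
| 14.9, first | 75.2% | no | yes | no |
| 10, first | 83.3% | no | yes | no |
| 10, preceding value also < 15 | 83.3% | no | yes | yes |

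Baselines of 51, 80 and 100 give the same answers below 15.

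**Which condition blocks rule A?** The smallest fall from above 50 to below 15 exceeds (50 − 15)/50 = 70%. The 20% condition is therefore always met, and only the floor at 15 switches rule A off.

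**A second disagreement between A and B.** A fall from 51 to 45 is (51 − 45)/51 = 11.8%. Rule B reduces and rule A does not. The note thus differs from Section 5.3.1 at both ends.

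**When could a second value arrive without a special repeat test?** On-site checks are at months 1, 3, 6, 9 and 12, so the gaps from randomization are 1, 2, 3, 3 and 3 months. At 30.4 days a month, the longest is 3 × 30.4 = 91 days, or 91 + 14 = 105 days with a 7-day window at each end.

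**Other text that could supply an action after one low value**
- Section 5.7 requires action for other label contraindications. It allows a newly met exclusion criterion to lead to interruption or discontinuation only where the labels make it a contraindication. The labels are not in the documents.
- Section 4.3.1, item 3 covers severe laboratory abnormalities, on the investigator's judgement.
- Section 9.5.1 has laboratory results assessed for clinical significance and isolated abnormal results reported as adverse events. For each event, the investigator decides whether to interrupt or stop study drug.

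These are routes to a decision. None is a stated action tied to a CrCL value.

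**The case against.** The strongest reply is that the protocol does not leave such a subject unattended. Section 9.5.1 calls for a decision on study drug, Section 4.3.1 permits withdrawal, and Section 5.7 points to the labels, which may well settle the matter. This stands in part: it rules out saying that nothing in the protocol applies. It does not make the numeric rules agree, and the labels cannot be checked here.

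A reader might infer that the confirmatory test is timed to follow recovery, so that the stop rule can hardly operate. The text does not support that. The repeat is a recommendation for suspected transient falls only, corrective action is an alternative trigger to resolution, one example is as short as 1-2 weeks, and a scheduled visit can supply the second value.

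The Figure 3.1 note may be only a summary of dosing at entry, where values below 15 are excluded. If so, it does not conflict with Section 5.3.1 on this point, but no numeric rule then covers a first value below 15. If it does govern after randomization, it covers the case and contradicts Section 5.3.1. Either way the note's scope needs stating.

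The resumption sentence can be read as following the mandatory stop in the same paragraph. That explains what is being resumed, but leaves a stop called permanent that is reversible on recovery.

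**Conclusion.** The inconsistency is established from the text. For a first post-randomization CrCL below 15 mL/min, Section 5.3.1 and the mandatory stop in 5.7 order nothing, while the Figure 3.1 note, if it applies, reduces the dose. What applies between a first and a confirmatory value is not stated, and the permanent stop sits uneasily with the instruction to resume.

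Staying on full dose mainly concerns subjects still on 60 mg who fall by more than 70%, from above 50 to below 15, without a qualifying value in between. Subjects already reduced would be on 30 mg. A reader might go further and argue that, since the renal factor is defined as 15-50, a reduced subject who drops below 15 no longer has it and returns to 60 mg. The factor is described as moderate or severe renal impairment, so this cannot be taken as the intended reading.

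The consequence is patient safety and uniform conduct across sites. The effect on the hazard ratio is expected to be negligible, on the judgement that few of the 750 edoxaban subjects would have such a fall. The documents give neither the frequency of these falls nor the bleeding hazard during them, so a count of excess bleeds would rest wholly on assumed inputs and none is offered.

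**What to change.** Reconcile the synopsis dosing text, the Figure 3.1 note, Section 5.3.1 and Section 5.7, with the IXRS dose logic built on them:

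1. Every post-randomization CrCL value, including a single value below 15 mL/min, should fall under one consistent stated action.
2. State what applies to study drug between a first and a confirmatory value.
3. State whether the Figure 3.1 note applies after randomization or only at entry.
4. Resolve the conflict between a permanent stop and resumption on recovery.

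The clinical content, including any timing of the confirmatory test, is for the sponsor to decide. The cost is protocol wording and a check of the IXRS rules. CrCL is already obtained at each on-site visit, so the reconciliation itself needs no new assessment.
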